# 5.1.12 Pregnancy test (for females of child bearing potential)

See section 3.1.10.1 for definition.

## 5.1.13 Serologic Tests

HLA typing.

## 5.1.14 Radiographic Imaging

Bone scan, CT chest, abdomen and pelvis with IV contrast. MRI of brain with contrast, if tolerated. MRI of the abdomen should be considered on an individual basis if felt to be better by the radiation or medical oncologist. CT and Bone Scan must be performed within 21 days (+ 7 days) of registration.

#### 5.1.15 Biopsy of metastatic lesion

#### 5.1.15.1 **Pre-treatment biopsy:**

A CT-guided biopsy of a tumor lesion will be performed prior to study registration, unless previous biopsy of metastatic site within the last six months exists and a review of slides shows it to be adequate, in which case a pretreatment biopsy is optional. Soft tissue lesion will be preferred over bone biopsy for the pre-treatment biopsy. Biopsy results do not affect eligibility if previous diagnosis of clear cell histology is present. If the patient participated in protocols [such as the Urology Tissue Repository Protocol (STU 032011-187)] or procedures and the tissue confirming kidney cancer diagnosis is in storage and available at UTSW Medical

Center or an outside institution, the study team may request a tissue sample.

## 5.1.15.2 Post-treatment elective biopsy:

An elective post-treatment biopsy will be performed 8 weeks after the completion of HD IL-2 and for this biopsy, any site other than a lymph node and a treated site is acceptable. In the case where all lesions are treated, any progressive or non-responding lesion will be biopsied. In case of CR no lesions may remain to be biopsied.

## 5.1.16 QoL Questionnaires

FACT-G, EQ-5D, FKSI, cost and convenience questionnaire. These forms will be referred to collectively as QoL Questionnaires. Cost and convenience questionnaire will only be completed at first follow-up.

## 5.1.17 Tumor assessment

To be performed on bone scan, CT or MRI. Please see section 6.1 for detail.

#### 5.1.18 Pulmonary Function Tests

#### 5.1.19 Cardiac Stress Test

## 5.2 Procedures During Treatment

SABR treatment requires one week for planning and one week for delivery of the 1 or 3 fractionation schemes. HD IL-2 must begin within 84 hours of the last SABR fraction. Each course of HD IL-2 consists of two cycles of approximately two weeks each (12-14 IV infusions q8h followed by about 9 days of break) requiring a total of four weeks.

## 5.2.1 Prior to Each Treatment Cycle

- Physical exam, vital signs
- Hematology
- Serum chemistries

#### 5.2.2 Prior to treatment

- Registration to the study (registration must be done prior to first fraction of SABR)
- CT simulation for SABR planning.
- If multiple planning sessions are required, they will be completed within the first week. SABR planning completed

## 5.2.3 Day 1-14 (+/- 7days)

- SABR treatments completed
- One hour after first SABR treatment, blood collection for correlative studies
- If SABR to multiple sites, an additional 5 days is allowed to complete treatment

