#### 1.4.1 Immunologic Rationale

There are multiple immunologic steps where SABR is expected to augment the immune response generated by IL-2 and vice versa. As discussed above, IL-2 stimulates T cell-mediated immune response in a non-specific manner. It is expected that SABR, inducing immunogenic tumor cell death, will be able to provide a specific direction to the immune response by initiating antigen presentation. Recruited and activated by the DAMPs and other changes brought on to the tumor micro-environment by radiation therapy, the APCs migrate to the lymph node for antigen presentation and T-cell activation. This is one of the first steps that will be augmented by the administration of IL-2 since the presence of IL-2 is critical for the successful activation of T cells by DCs [26, 28]. It is estimated that this step will take 2-3 days, which is why IL-2 treatment will be initiated within 2-3.5 days of SABR.

RT also increases TIL trafficking within irradiate tumors [12, 20]. IL-2 increases tumor vascularization, thereby decreasing hypoxia within tumors and making them more radiosensitive [40]. The radiosensitizing effect of IL-2 gene expression within tumors has also been objectively demonstrated *in vivo [41]*. The effect of increased vascularization by IL-2 also is expected to increase TIL and APC infiltration within all tumor sites. IL-2-mediated increase in CTL trafficking to the tumor sites, as described above, will work synergistically with this step in increasing TIL in both irradiated and non-irradiated sites of tumor.

The combination of RT and cytokine therapy with macrophage inflammatory protein-1 $\alpha$  has been shown to induce strong abscopal effect regardless of tumor type [42]. In fact, the combination of IL-2 and RT has also been explored in animal models and has shown improved local control of irradiated tumor and regression of non-irradiated tumors within the same mouse [43, 44].

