Enhancements of increased cytotoxicity to renal cancer cells can be measured by cytotoxicity assays. Antibody-dependent cell-mediated cytotoxicity (ADCC) measures the cell-killing ability of certain lymphocytes that require the target cell to be marked by an antibody and thus measures the humeral response [28]. On the other hand, lymphocyte-mediated cytotoxicity assay will measure the formation of tumor-specific CTLs among the lymphocytes collected from patients with the controls being lymphocytes collected from the same patients before SABR and before HD IL-2. Since it is not practical or feasible to obtain sufficient quantities of tumor cells from each patients to assess a quantitative cytotoxicity by these assays, established allogenic human human renal cancer cell line Caki-2 and ACHIN will be used for this purpose. It is a generally accepted principle of tumor immunology that there will be many common tumor antigens between different patient tumors of same site origin, and therefore tumor cell lines as well [28]. In fact, the tumor antigens (PSA, CEA, CA 19-9 etc.) that are in clinical practice are reported to be present in a significant portions of patients of the respective tumor site. This concept of commonality of tumor antigens between allogenic tumor cell lines and patients is put into clinical practice by the GVAX anti-tumor vaccine which is currently in early phase clinical trials for pancreatic, melanoma and renal cancer [62, 63]. GVAX consists of multiple human tumor cell lines of the respective site, that is modified to express GM-CSF, and killed with radiation prior to injection in patients. The presence of common tumor antigens in the cell lines and patient's tumors, leads to induction of an immune response. The LNCaP and PC-3 cell lines has been shown to express many of the common renal cancer antigens, and therefore, is an appropriate surrogate to be used instead of patient's own cells and has been used in similar in vitro cytotoxicity assays [64-68].

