Cytokines are hormonal messengers responsible for most of the effects in the immune system such as activation of innate versus adaptive immune response, cellular versus humeral immune response [69, 70]. For example, an increased level of IL-2 and IFN- $\gamma$  suggests activation of Th1 cells leading to activation of macrophages and suggests a cell-mediated adaptive immune response whereas IL-4 and IL-5 may indicate Th2 activation and induction of humoral immunity [28, 70]. An increase in IL-17 may suggest activation of autoimmune responses [71]. Therefore, measurements of serum cytokine levels have generally been used previously in clinical trials as surrogates to assess specific activation of immune pathways [72, 73]. Serum cytokines from this clinical trial before and after SABR will be measured using an extensive array of cytokines to explore the specific immune pathways that are initiated by SABR. The planned array of cytokines will measure levels of the following cytokines before and after treatment for each patients: Th1/Th2/Th17 cytokines: IFN- $\gamma$ , IL-1 $\beta$ , IL-2, IL-4, IL-5, IL-8, IL-10, IL-12p70, IL-13, IL-17 TNF- $\alpha$ ; pro-inflammatory cytokines: GM-CSF, IFN- $\gamma$ , IL-1 $\beta$ , IL-2, IL-6, IL-8, IL-10, IL-12p70, TNF- $\alpha$ ; Chemokines: Eotaxin, MIP-1 $\beta$ , TARC, IP-10, IL-8, MCP-1, MCP-4, KC, and others including IL-6, IL-12, TGF- $\beta$  and HMGB1.

Many surrogate markers for activated and proliferating lymphocytes have been described. Some of these markers include CD25, CD71, CD45RO, CD107a, CD54, CD69, Ki67 and ICOS/CD278 [74-77]. These markers are easily measured with antibodies specific for the markers that are tagged with a fluorophore utilizing FACS analysis. Also using FACS, activation markers on other immune cells such as CD80 and CD 86 on DCs, and inhibitory markers on monocytes such as PD-1 can be measured as surrogates of immune activation or inhibition. These measurements from PBMCs collected from patients before and after treatment will give us further information

regarding the intensity of the immune response. Additionally, PD-L1, the ligand of PD-1, often expressed in tumor cells, can be quantified from patient pre-treatment tumor biopsy.

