## 4.0 TREATMENT PLAN

#### 4.1 SABR Dose and Techniques

#### 4.1.1 SABR Dose

The SABR dose and fractionation scheme is generated to deliver a potent dose to ablate the targeted lesions and at the same time maximize an immune response. Since multiple studies have shown an influx of lymphocytes and monocytes within 24-48 hours after tumor irradiation [7, 12, 13, 92] and these cells play a critical role in antigen presentation and initiation of an adaptive immune response, multiple fraction irradiation which would kill these infiltrating immunocytes, is discouraged. Therefore a single fraction or a three fraction treatment regimen is allowed, and a single fraction treatment is preferred over three fractions. Due to normal organ toxicity and limits of dose constraints, sometimes a three fraction treatment must be undertaken and in those cases it is recommended that the treatment course is completed within 7-10 days. Radiation dose-(immune) response studies have shown a linear increase in immune response with increased dose per fraction of radiation without demonstration of a plateau [12, 14, 92, 93]. Two studies have compared 15Gy x 1 with 5Gy x3, and 20Gy x1 with 5Gy x4 and have showed a superior immune response generated by the single fraction radiation [12, 92]. Clinical experience with oligometastatic patients treated at 1-5 sites of disease has also showed an increase in progression free survival with the increasing radiation dose per fraction [94]. A dose of less than 7.5 Gy per fraction has demonstrated lower induction of systemic IFN-y producing cells [93], and a previous phase II study of mRCC patients treated with HD IL-2 and singe fraction of 8Gy

irradiation to a single lesion did now show an overall improvement in response rate [95]. Therefore 8Gy per fraction is the lowest permitted dose for this study and can be used only when administering the three fraction regimen as described in the prescription dose table below.

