## 5.2.6 Day 30-37 (+/- 14 days)

- Physical exam, vital signs
- Hematology
- Serum chemistries
- Second cycle of HD IL-2
- Blood collection for correlative immunologic studies (see section 9.0) on the last day of HD IL-2

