# 9.0 CORRELATIVES/SPECIAL STUDIES

The goal of the planned laboratory correlative studies is to measure the induced immune response to patient's pre-treatment tumor tissue antigens (see section 1.5 for detail). In addition, the correlative studies will evaluate the immune response generated by the regiment. The submission of collected whole blood before, during and post treatment as indicated in Section 5 is mandatory and will be performed at baseline, during RT (one hour after first SABR fraction), after HD IL-2 cycle 2, at 8 weeks, 6 months and 1 year. Biopsy specimen of metastatic sites prior to initiation of treatment is required if previous biopsy of metastatic site within six months with adequate review of slides is not performed or available, in which case it is optional. If the patient participated in protocols [such as the Urology Tissue Repository Protocol (STU 032011-187)] or procedures and the tissue confirming kidney cancer diagnosis is in storage and available at UTSW Medical Center or an outside institution, the study team may request a tissue sample. The 8wks post-treatment biopsy is optional.

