# 11.3 Data Analyses Plans

This is a single-arm Phase II trial of SABR and HD IL-2 for mRCC patients. PFS and OS, will be estimated using the Kaplan-Meier approach along with the 95% confidence interval. Exact binomial method will be used to calculate the response rate, toxicity and the corresponding 95% confidence interval. One-sample log-rank test [121] will be used to test if the survival endpoints such as OS or PFS are significantly different from those in the historical control reported in McDermott et. al [35].

Generalized estimating equation (GEE) analysis will be conducted to test if the median number of spots in Elispot of the PBMC collected from patients are significantly different over time (before starting of treatment and after SBRT, at 8 weeks and six months). T-Cell proliferation SI will also be evaluated in the same manner.

HRQol, CEA and quality adjusted survival time analysis is described in Section 10.

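### For the cellular and antibody assays, the only post-SABR, pre-IL-2 blood sample is taken one hour after the first fraction, so the after-SBRT time point is close to a second baseline

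*Combined protocol and SAP*

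**What the plan says.** **Schedule.** Section 5.2.3 places the post-SABR sample early: "One hour after first SABR treatment, blood collection for correlative studies". Section 9.0 makes blood submission mandatory and has it "performed at baseline, during RT (one hour after first SABR fraction), after HD IL-2 cycle 2, at 8 weeks, 6 months and 1 year". Section 9.1.1 gives the same times and reduces the one-hour EDTA volume to 20 ml, against about 100 ml at the other visits. The next sample is set in Section 5.2.6: "Blood collection for correlative immunologic studies (see section 9.0) on the last day of HD IL-2", meaning the second cycle. In the Section 5.4 table the immune-assay row is blank at Cycle 1 Day 15. Its footnote # lists a post-SABR sample without a time.

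**Kinetics.** Section 4.1.1 states that "multiple studies have shown an influx of lymphocytes and monocytes within 24-48 hours after tumor irradiation". Section 1.4.1 (Immunologic Rationale) describes migration of antigen-presenting cells to the lymph node, antigen presentation and T-cell activation, and says: "It is estimated that this step will take 2-3 days, which is why IL-2 treatment will be initiated within 2-3.5 days of SABR".

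**Aims and analysis.** Section 1.5 wants cytokines measured before and after SABR "to explore the specific immune pathways that are initiated by SABR". For the cytotoxicity assay it names as controls: "controls being lymphocytes collected from the same patients before SABR and before HD IL-2". Section 2.4.4 defines immune response by ELISpot, T-cell proliferation and ELISA. Section 11.3 tests ELISpot by GEE over four times, "before starting of treatment and after SBRT, at 8 weeks and six months", and treats the proliferation index in the same way.

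**The concern.** The protocol times the start of IL-2 to the biology that SABR is expected to set off, but samples blood long before that biology is due. If the sample precedes the response, ELISpot, proliferation, ELISA, cytotoxicity and FACS readings at that point should look much like baseline whether or not SABR primes anything. The next GEE time is 8 weeks, after two IL-2 cycles, so any change seen there belongs to SABR and IL-2 together.

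At stake is the one within-patient contrast that could show a cellular or antibody effect of SABR alone. The trial has no IL-2-alone arm, and no biopsy is planned between SABR and IL-2 (the post-treatment biopsy is elective, 8 weeks after IL-2). Nothing else in the plan can supply that contrast.

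**Working it through.** The plan states no figure on this point that could be reproduced. The check compares scheduled times with the protocol's own kinetics.

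**Inputs**
- Draw: 1 h after the first fraction (5.2.3, 9.0, 9.1.1).
- Cell influx: 24-48 h after irradiation (4.1.1).
- Antigen presentation and T-cell activation: 2-3 days = 48-72 h (1.4.1).
- IL-2 start: 2-3.5 days = 48-84 h after SABR (1.4.1). Sections 4.1.3, 4.2 and 5.2.4 give only the 84 h maximum.
- Three-fraction course: completion within 7-10 days is recommended (4.1.1). I take this as the time from first to last fraction, which is an assumption.

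**Step 1: which sample is the after-SBRT point?** The scheduled samples are baseline, one hour after the first fraction, end of IL-2 cycle 2, 8 weeks, 6 months and 1 year. Only the second lies after any SABR and before IL-2. It must therefore be the post-SABR sample of the 5.4 footnote and the after-SBRT time of 11.3.

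**Step 2: lead time of the draw = start or end of window minus 1 h**
- Influx: 24 − 1 = 23 h; 48 − 1 = 47 h.
- Presentation step: 48 − 1 = 47 h; 72 − 1 = 71 h.

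**Step 3: unsampled interval from the draw to IL-2 = course length + interval to IL-2 − 1 h**
- Single fraction: 48 − 1 = 47 h to 84 − 1 = 83 h.
- Three fractions: 7 × 24 + 48 − 1 = 215 h to 10 × 24 + 84 − 1 = 323 h, about 9 to 13 days. At the draw, one of three fractions has been given. With several sites, some may still be untreated, since 5.2.3 allows 5 more days for them.

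**Step 4: where a pre-IL-2 draw would fall.** Appendix C starts IV fluids at least 1 h, and preferably 4 h, before the first dose. A draw just before hydration falls between 48 − 4 = 44 h and 84 − 1 = 83 h after the last fraction, if IL-2 starts within the 1.4.1 range. That is inside or past the influx window, and from shortly before the presentation step to past it. The Appendix C order has the first dose at 15:00, so even with 4 h of fluids the draw is due by about 15 − 4 = 11:00.

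**Step 5: volumes (9.1.1).** One-hour draw: 20 + 20 = 40 ml. Standard draw: about 100 + 10 = 110 ml.

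**The case against.** The other side has several good points.

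- **The objectives do not ask for the separation.** Objective 2.2.6 concerns treatment-related response and 2.3.1 concerns correlates or predictors of treatment response. Section 9.0 speaks of the response to the regimen as well as to tumor antigens. The other samples serve all of these. A reader might infer that the two objectives cannot be met; their wording does not support that. The SABR-specific aims stand only in Section 1.5.
- **The kinetics are those of tumor and lymph node.** They give no time course for soluble mediators in blood, and the 4.1.1 wording allows influx to begin before 24 h. The SABR-specific cytokine aim and its panel, which includes HMGB1, could be served at one hour. The one-hour draw is in fact weighted towards serum (20 ml against 10 ml). The inference that it is too early for everything therefore fails. Likewise, dividing 24-72 h by 1 h gives a ratio of times, not an effect size.
- **Later confounding comes from the single-arm design.** A reader might hope that a better-timed draw would separate SABR from IL-2 throughout. It would not do so once IL-2 has started.
- **The control may not be missing.** A sample taken before both treatments could be the single baseline sample, so Section 1.5 does not clearly promise two.
- **No decision rule exists.** Section 11.3 does not say that a null result at this point means SABR failed to prime a response.
- **A later draw may also be null.** Section 1.4.1 treats IL-2 as critical to T-cell activation.

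What remains unanswered is narrower. For the cellular and antibody assays, nothing in the documents leads one to expect a response at one hour, yet 11.3 analyses two of them at that point.

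**Conclusion.** The point holds for ELISpot, T-cell proliferation, ELISA, cytotoxicity and FACS. Their only SABR-only sample comes 23-47 h before the protocol's influx window and 47-71 h before its presentation step. In three-fraction patients it also comes before two of the three fractions. The after-SBRT time in 11.3 is close to a second baseline for these assays, and no patient has a SABR-only sample later than one hour.

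This rests on the protocol's own kinetics and on treating tissue-level times as a guide to when cells and antibodies in blood could change. It weakens the mechanistic aims of Section 1.5. It leaves the primary response-rate analysis untouched. It is a low-cost improvement worth making, not a flaw in the trial's main conclusion.

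**What to change.** **Change**
- In 5.2.3 and 5.2.4, 5.4 (Cycle 1 Day 15 column and footnote #), 9.0 and 9.1.1, move the EDTA/PBMC draw to the IL-2 cycle 1 admission. Take it after the last SABR fraction and before IV hydration, premedication and the first IL-2 dose. Schedule it in laboratory hours, so that the 2-hour processing limit in 9.1.1 can be met.
- In 11.3, name this sample as the after-SBRT point. In 1.5, say whether it is also the pre-IL-2 control.
- Keep the one-hour draw as serum only, for soluble mediators. Section 9.2.7 is headed serum but describes plasma, so state which is used and compare like with like.
- Record hours from the first and from the last fraction to the draw. The interval to IL-2 has an 84 h maximum but no operative minimum, so it will vary.

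Treatment timing need not change.

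**Cost.** Amendment wording and no extra visit: hematology and chemistry are already drawn at this admission and a central line is placed. The pre-IL-2 draw becomes about 110 ml instead of 40 ml, a difference of 110 − 40 = 70 ml. If the one-hour serum volume of 20 ml is kept, the total increase is 70 + 20 = 90 ml. The one-hour PBMC sample is lost, timing will differ between patients, and T-cell readings before IL-2 may still be small.

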#### 5.2.4 Day 15-22 (+/- 7days)

- Physical exam, vital signs
- Hematology

- Serum chemistries
- First cycle of HD IL-2 started within 84hr of the last SABR treatment

## 5.2.5 Day 22-29 (+/- 7days)

- Break
- Patient will be assessed either by clinic visit or telephone call to ensure s/he is doing well and ready for the second cycle. Telephone call can be done by any clinic staff or study personnel.

## 5.2.6 Day 30-37 (+/- 14 days)

- Physical exam, vital signs
- Hematology
- Serum chemistries
- Second cycle of HD IL-2
- Blood collection for correlative immunologic studies (see section 9.0) on the last day of HD IL-2

#### 5.2.7 Week 8 (+/- 2 weeks)

- Physical exam, vital signs
- Hematology
- Serum chemistries
- QoL questionnaire
- Blood collection for correlative immunologic studies (see section 9.0)
- Radiographic imaging
  - $\circ$  CT chest, abdomen and pelvis with IV contrast, if soft tissue metastasis
  - Bone scan if bone lesion was present and detected by the baseline Bone scan
  - MRI, if necessary to confirm CT/bone scan findings, at the discretion of radiologist

#### 5.2.8 Weeks 8-45 from registration date

 HD IL-2 can be repeated for a maximum of 3 courses 12 weeks apart at the discretion of the medical oncologist

#### 5.3 Follow-up Procedures

Subject will be followed every eight-ten weeks (+/- 2 Weeks) starting from the date of registration for the first eight months, then every 12 weeks until 18 months and then every sixteen weeks for another three years and then every three – six months for the next five years. Thereafter at the discretion of the treating physician. The following procedures will be performed at each follow up:

- Physical exam, vital signs
- Hematology
- Serum chemistries
- QoL questionnaire (every other follow up)
- Blood collection for correlative immunologic studies (see section 9.0) Radiographic imaging
  - $\circ$   $\,$  CT chest, abdomen and pelvis with IV contrast, if soft tissue metastasis
  - Bone scan if bone lesion was present and detected by the baseline Bone scan
  - MRI, if necessary to confirm CT/bone scan findings, at the discretion of radiologist

	Pre-study	Cycle 1 , Day15 (+/- 5)	Cycle2, Day30 (+/- 14)	Cycle2, Day37 (+/- 14)	Months 1-8: q8 Weeks	Months 8-18: q12 Weeks	Months 18- 120: 3-6 months
Assessment	Х				Х	Х	Х
Informed Consent	Х						
Vital Signs	Х	Х	Х	Х	Х	Х	Х
History and PE	Х				Х	Х	Х
Performance Status	Х				Х	Х	X
Toxicity (include DLT) Evaluations	Х				Х	Х	Х
Bone Scan	Х				X*	X*	Х
CT Chest, Abd, pelvis w/ Contrast	Х				Х	Х	Х
Biopsy of metastatic lesion	Χ^				X@		
CBC with diff	Х	X 	X 	X 	Х	Х	Х
Basic Chemistry	X	X 	X 	X 	Х	Х	Х
Comprehensive chemistry	Х			Х	X&		
Blood collection for Immune Assays	Х			Х	X#	X#	X#
QOL Questionnaires	Х			X%	X%	X%	X%
Cardiac Stress Test	Х						
PFT	X						

